## Method

### Study design

The study is designed as a Phase 1/2a single-centre, double-blind, dose escalation, age de-escalation trial in malaria-exposed Malian adults and children. Two sequential stages of clinical research are conducted, each recruiting a distinct cohort of participants to confirm: 1. TB31F safety and 2. TB31F efficacy. Pharmacokinetic measurements will be performed in both safety and efficacy cohorts.

In total, a minimum of 165 participants will be recruited and enrolled; 45 adults and 30 children for the safety study, and ≥ 90 adults and children for the efficacy study. In the tables below, the cohorts are described with the number of participants, the duration of follow-up and the dose of TB31F administered.

*Table 1. Study design for Cohort 1 (Adults): Safety and pharmacokinetics (18-50 years of age)*

Group	Dose	N	Volume TB31F/Saline	Sample timepoints*	Safety follow-up after each dose administration
1	1A: Control (normal saline)	5	0.2 mL	Day 0 (Baseline), 1, 5, 7, 14, 21, 28, 42, 56, 84	Solicited local and systemic AEs (days 1-7); Unsolicited AEs (study duration); SAEs (study duration)
	1B: 10 mg mAb TB31F	10			
2	2A: Control (normal saline)	5	2 mL		
	2B: 100 mg mAb TB31F	10			
3	3A: Control (normal saline)	5	4 mL		
	3B: 200 mg mAb TB31F	10			

\* Group 1 participants will be followed-up until day 28

*Table 2. Study design for Cohort 1 (Children): Safety and pharmacokinetics in school age children (>10-15 years)*

Group	Dose	N	Volume TB31F/Saline	Sample timepoints	Safety follow-up after each dose administration
4	4A: Control (normal saline)	5	0.2 mL	Day 0 (Baseline), 1, 5, 7, 14, 21, 28, 42, 56, 84	Solicited local and systemic AEs (days 1-7); Unsolicited AEs (study duration); SAEs (study duration)
	4B: 10 mg mAb TB31F	10			
5	5A: Control (normal saline)	5	2.0 mL		
	5B: 100 mg mAb TB31F	10			

*Table 3. Study design for Cohort 2: Efficacy in a mixed age cohort (>10-50 years of age)*

Group	Dose	N	Volume TB31F/Saline	Sample timepoints	Safety follow-up after each dose administration
6.1	6AB: Control (normal saline)	15	0.6* mL	Day 0 (Baseline), 1, 5, 14, 21, 28, 56, 84	Solicited local and systemic AEs (days 1-7); Unsolicited AEs (study duration); SAEs (study duration)
	6B: 30 mg mAb TB31F	30	0.6* mL		
6.2	6AC: Control (normal saline)	15	2.0 mL		
	6C: 100 mg mAb TB31F	30	2.0 mL		

AE = Adverse events, SAE = Serious adverse events. Participants will be randomised in a 1:2:1:2 ratio to the 6AB, 6B, 6AC, or 6C group.

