#### Efficacy outcome measures related to within-group % reduction in proportion infected mosquitoes:

8. Group averaged within-individual percent reduction in the proportion of mosquitoes infected at day 5 post-treatment relative to baseline (day 0), assessed through direct membrane feeding assays (DMFA) and measured as oocyst prevalence (timeframe: day 0 [baseline] & 5)
9. Group averaged within-individual percent reduction in the proportion of mosquitoes infected in DSF, at all feeding timepoints relative to baseline (day 0). Comparisons of these reductions between groups at each post-baseline timepoint and comparisons of the reductions between post-baseline timepoints for each group (timeframe: day 0 [baseline], 1, and 5)
10. Group averaged within-individual percent reduction in the proportion of mosquitoes infected in DMFA, at all feeding timepoints relative to baseline (day 0). Comparisons of these reductions between groups at each post-baseline timepoint and comparisons of the reductions between post-baseline timepoints for each group (timeframe: day 0 [baseline], 1, 5, and 14)

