### Efficacy outcome measures

#### **Efficacy outcome measures related to within-group % reduction in proportion infected mosquitoes:**

We will determine averaged within-individual percent reduction in the proportion of mosquitoes infected at days post-treatment (1, 5, 14) compared to baseline (day 0) for each group. This will be assessed through DMFA and DSF and outcomes for these different feeding assays will be presented separately as percentage reduction (with 100% as total reduction of transmission, and negative values as enhanced transmission) with 95% confidence interval. Data will be analysed for all individuals who received the product per protocol and only for those individuals who are infectious at baseline (i.e. infecting at least one mosquito with any number of oocysts). All analyses on within-individual percentage reduction in the proportion of infected mosquitoes will use a mixed effects generalized linear model assuming a binomial error structure and a log-link, using individual mosquito data with day of follow-up and dose of TB31F and their interaction as fixed effects. A random intercept will be added to models to allow for participant-level variation in pre-intervention transmissibility and thus account for the correlation between outcomes for mosquito samples from the same participant (i.e. intra-cluster correlation).

In exploratory analyses, these analyses will be performed following stratification for naturally acquired transmission reducing immunity, as quantified by SMFA at baseline (pre-TB31F administration) samples.

The impact of naturally acquired transmission reducing immunity, assessed in baseline samples by SMFA (TRA>50%; TRA>80%) and by antibody prevalence to known gamete antigens Pfs230 and Pfs48/45, on infecting mosquitoes will also be determined. For this, TRA as categorical variable and antibody prevalence (binary variable), will be added as fixed effects to mixed effects logistic regression models on proportion infected mosquitoes at baseline (pre-TB31F administration). These models may be expanded to include human genetic factors (e.g. a fixed effect for HbAS or HbAC carriage as compared to wild-type HbAA).

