#### **Efficacy outcome measures related to mosquito infection intensity (oocyst density):**

In this analysis, we do not assess reductions in infection intensity but present the average oocyst density at each timepoint for each arm. Data will be presented for DMFA and DSF separately.

We will fit a mixed effects negative binomial regression model with fixed factors time and study arm and their interaction and individual-specific random intercepts to estimate average oocyst densities at each timepoint for each arm and compare prevalence estimates between time-points for each arm and between arms for each time-point using oocyst density ratios (and 95% CIs).

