#### **Efficacy outcome measures related to transmission reducing activity (reductions in oocyst intensity):**

We will determine averaged within-individual percent reduction in the density of oocysts at days post-treatment (1, 5, 14) compared to baseline (day 0) for each group. This will be assessed through DMFA, DSF and SMFA and outcomes for these different feeding assays will be presented separately as percentage reduction (with 100% as total reduction of transmission, and negative values as enhanced transmission) with 95% confidence interval. For DMFA and DSF, these data will be analysed for all individuals who received the product per protocol without restrictions to baseline infectivity, and for those individuals who are infectious at baseline (i.e. infecting at least one mosquito with any number of oocysts). For SMFA, these data will be analysed for all individuals who received the product per protocol without restrictions to baseline infectivity in DMFA or DSF, as well as for the subset of individuals who are infectious at baseline. SMFA, an exploratory outcome, will be conducted after unblinding to allow testing of a realistic sub selection of test and control samples. Participants may have naturally acquired TRA due to exposure to gametocytes prior to enrollment; SMFA on baseline samples will allow us to identify these individuals. Additional samples that are most informative for determining the IC80 will be selected based on the ELISA data and tested in the SMFA. For this, one person not involved in data analysis will be unblinded and select samples based on ELISA values and treatment arm.

All analyses on within-individual percentage reduction in oocyst density will use a mixed effects negative binomial regression model with day of follow-up and dose of TB31F as fixed effects. A random intercept will be added to models to allow for participant-level variations (i.e. intra-cluster correlation).

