### Outcome measures related to estimated inhibitory concentrations:

Transmission blocking activity (TBA, the reduction in the proportion of infected mosquitoes) and transmission reducing activity (TRA, the reduction in oocyst numbers/infection intensity) will be determined for DMFA and DSF separately. Baseline infection prevalence and intensity estimates will be used to calculate relative reductions in these transmission measures during follow-up. For SMFA experiments, TRA will be quantified as the relative reduction in oocyst intensity for test samples (one feeder per test sample) compared to pooled naïve serum controls (two feeders). Samples may be tested in one or two independent SMFA experiments.

TRA values for each participant and time-point will be estimated using mixed effect negative binomial regression models with random intercepts for each experiment to account for between experiments differences in oocyst intensity that is achieved in control experiments (SMFA) or baseline measurements (DMFA/DSF).

TBA values for each participant and time-point will be estimated using mixed effect logistic regression models with random intercepts for each experiment to account for between experiments differences in oocyst prevalence that is achieved in control experiments (SMFA) or baseline measurements (DMFA/DSF). Of note: for SMFA TBA estimates are deemed to be less informative than TRA estimates due to the design of these experiments that aim for high oocyst prevalence and density in control experiments.

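### The model for percent reduction in oocyst density omits the day-by-dose interaction, so it gives every arm the same reduction

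*SAP*

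**What the plan says.** The SAP's analysis section on transmission reducing activity (reductions in oocyst intensity) defines its target as the averaged within-individual "percent reduction in the density of oocysts at days post-treatment (1, 5, 14) compared to baseline (day 0) for each group", to be given separately for DMFA, DSF and SMFA with 95% confidence intervals. The closing paragraph of that section then states that all analyses of this kind "will use a mixed effects negative binomial regression model with day of follow-up and dose of TB31F as fixed effects". A random intercept allows for differences between participants. The section names no interaction, no random slope on day and no separate fit by arm.

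The neighbouring sections are written differently:

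- Percent reduction in proportion infected, the direct counterpart for prevalence: "using individual mosquito data with day of follow-up and dose of TB31F and their interaction as fixed effects".
- Oocyst density, which has the same outcome and model family: "mixed effects negative binomial regression model with fixed factors time and study arm and their interaction and individual-specific random intercepts".
- Mosquito infection prevalence and participant infectivity: both logistic models also include the time-by-arm interaction.

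For the efficacy cohort, Study design states: "Participants will be randomised in a 1:2:1:2 ratio to the 6AB, 6B, 6AC, or 6C group". With the numbers in Table 3 this is 15 + 15 controls, 30 on 30 mg and 30 on 100 mg.

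**The concern.** The stated estimand is a change from baseline in each arm. A model with day and dose as main effects has one set of day effects shared by all arms. Its dose term is a constant shift in level on every day, including day 0, before any product has been given. It therefore describes arms that start at different levels and then move in parallel, whereas a randomised trial of an active product should see arms that start level and then diverge.

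If the model is fitted as written, the control arm is credited with a reduction it did not have and the most active dose is understated. A weaker dose can be overstated. No difference in reduction between arms can appear, whatever the data show. Outcome 20, listed under the same heading among the outcome definitions, asks for comparisons of TRA within groups against baseline and between groups, and this model could not support them.

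**Working it through.** **Plan's own figure.** The SAP gives no power, precision or expected value for oocyst density, so there is none to reproduce. Its sample size section concerns the proportion of infected mosquitoes, and nothing below depends on it.

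**Step 1: algebra.** Take the usual log link for a negative binomial model, with t for day, g for dose group and i for participant:

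log E(y) = b0 + day(t) + dose(g) + u(i), with day(0) = 0.

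The ratio of day t to day 0 for a participant in group g is

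exp[b0 + day(t) + dose(g) + u(i)] / exp[b0 + dose(g) + u(i)] = exp[day(t)].

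Both dose(g) and u(i) cancel. The percent reduction is 100 × (1 − exp[day(t)]) in every arm. This holds whether dose is categorical or linear in mg, and it does not depend on the data.

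With the interaction, the ratio is exp[day(t) + day×dose(t,g)], which is free to differ by arm. With control as reference it is exp[day(t)] for control.

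**Step 2: rough size by hand.** If the three arms weighed equally on the log scale, the common ratio would be the geometric mean of the true ratios.

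- True reductions 0/90/90%: (1 × 0.1 × 0.1)^(1/3) = 0.215, a common reduction of 78.5%.
- True reductions 0/60/90%: (1 × 0.4 × 0.1)^(1/3) = 0.342, a common reduction of 65.8%.

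**Step 3: simulation of the actual model.** From the SAP: 30 per arm (controls pooled, 15 + 15), 40 mosquitoes per feed, DSF on days 0, 1 and 5, DMFA on days 0, 1, 5 and 14. Assumed, because the SAP gives no values: baseline mean of 1, 3, 10 or 30 oocysts per mosquito, negative binomial k of 0.2 or 0.5, participant SD of 1 on the log scale, and the same reduction on all post-dose days. The random-intercept negative binomial model was fitted by adaptive quadrature, with 20 replicates per setting. Entries are the minimum to maximum day-5 reduction (%) over this grid.

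| Assumed truth (control / 30 mg / 100 mg) | As written, DSF days | As written, DMFA days | With interaction |
|---|---|---|---|
| 0 / 90 / 90 | 74.2–82.1 in all arms | 76.2–83.3 in all arms | control −2.6 to 4.0; 90% arms 89.5–90.4 |
| 0 / 60 / 90 | 60.9–69.2 in all arms | 62.6–71.4 in all arms | control −2.6 to 4.0; 60% arm 58.8–61.4; 90% arm 89.5–90.4 |

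The interaction ranges are taken over both scenarios together.

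Under 0/90/90 the control arm reads 74–83% instead of 0%. Each dose reads low by 90 − 83.3 = 6.7 to 90 − 74.2 = 15.8 points. Under 0/60/90 the weaker dose is overstated by 60.9 − 60 = 0.9 to 71.4 − 60 = 11.4 points, and the stronger understated by 90 − 71.4 = 18.6 to 90 − 60.9 = 29.1 points.

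**Step 4: effects that vary by day.** One simulated data set used 2 oocysts per mosquito at baseline, participant SD 1 and k 0.5, with true reductions at days 1/5/14 of 0/0/0%, 80/80/70% and 95/95/90%.

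- As written: 76.4/75.8/71.7% in all three arms.
- With the interaction: control −3.8/−4.8/−1.0%, 30 mg 79.7/78.7/69.8%, 100 mg 94.7/94.3/89.7%.
- −2 log-likelihood falls from 44370.1 to 43380.1, a drop of 990.0 for 3 × 2 = 6 added parameters.

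**The case against.** The strongest reply is that the SAP already contains the right model. The oocyst density section fits time, arm and their interaction to DMFA and DSF counts and compares timepoints within each arm by density ratios; 100 × (1 − ratio) is the percent reduction wanted. That is true arithmetically and limits the harm. But that section says it does not assess reductions and does not cover SMFA, while the section at issue assigns all reduction analyses to its own model.

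The omission is also probably a slip of drafting, and identical figures in every arm would be noticed at once. That makes a published error less likely. It does not make the text right: under the SAP's Purpose section, deviations must be described and justified, so a later repair would itself be a deviation.

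Third, the section speaks of individuals who received the product, so controls may not be in the model. If they are not, the 0/90/90 example shows no bias, since both doses share 90%. Two doses with different effects would still be given one value. With 60% and 90%, the arithmetic mean of the ratios gives 1 − (0.4 + 0.1)/2 = 75% and the geometric mean gives 1 − √(0.4 × 0.1) = 80%, neither of which fits either arm. These are hand approximations, and the three-arm figures do not carry over.

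Coding dose as zero on day 0 would rescue dose-specific reductions, but the SAP does not say this, and it would hold the dose effect constant over days.

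Finally, reduction in oocyst density from day 0 by DMFA or DSF has no numbered outcome of its own, and the SAP treats secondary outcomes as hypothesis-generating. This bears on priority, not on correctness.

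**Conclusion.** The point holds. The model as specified cannot produce the per-arm reductions that its own section promises. The equality across arms is exact, given a log link, a pooled fit and dose coded as a fixed group characteristic. The percentages are illustrations: baseline density, dispersion, participant variation and the oocyst-density reductions are all assumed. The SAP's expected 90% reduction refers to infected mosquitoes, not to oocyst counts.

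The effect is confined to the oocyst-density reduction estimates in this one section, mainly DMFA and DSF. The primary day-5 DMFA prevalence analysis has the interaction. The density ratios also have it. The inhibitory-concentration section is separate too: there, "TRA values for each participant and time-point will be estimated using mixed effect negative binomial regression models". This should be corrected before analysis, but it does not threaten the primary result.

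**What to change.** In the analysis section on transmission reducing activity, specify day (categorical), dose group (categorical) and their interaction as fixed effects, in line with the sections on proportion infected and oocyst density. Report each arm's reduction as 100 × (1 − exp[day + day×dose]), which for control is 100 × (1 − exp[day]), and compare arms through the interaction terms. State whether the control participants enter the model and, if so, whether the two control sub-groups are pooled as the reference. Pooling is a convenient choice, but the correction does not depend on it.

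The cost is a few words in the SAP, with no change to data collection or sample size.

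### The SMFA oocyst-reduction model compares follow-up with day 0 without an experiment term or control feeders, so its interval is too narrow unless a participant's sera share a run

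*SAP*

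**What the plan says.** The SAP section on efficacy outcomes related to transmission reducing activity estimates the within-individual reduction in oocyst density "at days post-treatment (1, 5, 14) compared to baseline (day 0) for each group". It names the assays: "This will be assessed through DMFA, DSF and SMFA". The model is then fixed for all of them: "All analyses on within-individual percentage reduction in oocyst density will use a mixed effects negative binomial regression model". Its fixed effects are day and dose. The only random term is at participant level: "A random intercept will be added to models to allow for participant-level variations (i.e. intra-cluster correlation"). No experiment term and no control feeders are mentioned.

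On sample choice, the same section says that baseline sera are tested to identify natural activity, and adds: "Additional samples that are most informative for determining the IC80 will be selected based on the ELISA data and tested in the SMFA". It calls SMFA exploratory and places it after unblinding. The secondary efficacy objectives for Cohort 2, however, include SMFA transmission-reducing activity.

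Two other places treat SMFA differently. Outcome 20 defines the activity as a reduction against experimental controls. The section on estimated inhibitory concentrations compares each test sample (one feeder) with pooled naive serum (two feeders), allows one or two independent experiments per sample, and uses "random intercepts for each experiment to account for between experiments differences in oocyst intensity that is achieved in control experiments (SMFA").

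**The concern.** In SMFA the oocyst level depends partly on the laboratory run. The SAP accepts this in the section on inhibitory concentrations but leaves it out of the section that reports the group reductions.

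A participant intercept removes the run effect from a day contrast only when all of that participant's sera are fed in the same run. Otherwise part of the difference between day 0 and follow-up is a difference between runs, and nothing in the model's standard error reflects it. The section promises a percentage reduction with a 95% confidence interval for each group and reads negative values as enhanced transmission. A weak or strong run could therefore be reported as activity or enhancement with unjustified precision.

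Comparison with placebo does not reliably remove this. The reduction is reported per group, the additional samples are chosen partly by treatment arm, and nothing states that arms are balanced over runs.

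**Working it through.** **No plan figure to reproduce.** The SAP gives no precision or power for SMFA. Its Sample size section concerns the proportion of infected mosquitoes in DMFA and DSF.

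**Inputs.** From the SAP: 30 participants per TB31F arm (Table 3). Assumed, because the SAP does not give them: 20 mosquitoes per sample, mean 20 oocysts, negative binomial k = 2, and between-run SD of log intensity s = 0.3 to 0.5. The true effect is zero throughout, and one follow-up day is compared with day 0.

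**Standard error that the model would report** for the log ratio:

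SE = √[2 × (1/20 + 1/2) / 20 / 30] = √(1.1/600) = 0.043.

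**Run noise when day 0 and follow-up are fully split,** with R runs on each side: s × √(2/R). The total SD is √(run noise² + SE²). The chance that the nominal 95% interval excludes zero is 2 × [1 − Φ(1.96 × SE / total SD)].

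- R = 5, s = 0.3: run noise 0.190, total 0.195, chance 67%. Apparent reduction 1 − exp(±1.96 × 0.195), i.e. −46% to 32%.
- R = 5, s = 0.5: run noise 0.316, total 0.319, chance 79%. Apparent reduction −87% to 46%.
- R = 1, s = 0.3: run noise 0.424, total 0.426, chance 84%.
- R = 1, s = 0.5: run noise 0.707, total 0.708, chance 91%.

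**Simulation of three layouts.** The model had participant intercepts fitted as fixed effects, known dispersion and 150 replicates. Each cell gives the share of nominal 95% intervals excluding zero, then the central 95% range of the apparent reduction.

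| Layout, no experiment term | s = 0.3 | s = 0.5 |
|---|---|---|
| Both sera of a participant in one run | 4%; −9% to 7% | 5%; −7% to 8% |
| Samples at random over 6 runs | 23%; −16% to 14% | 40%; −24% to 19% |
| Fully split, one run each side | 85%; −153% to 55% | 91%; −319% to 77% |

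The fully split row agrees with the formula at R = 1 (84% and 91%).

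**With experiment terms and 40 control mosquitoes per run (two feeders):**

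| Layout | s = 0.3 | s = 0.5 |
|---|---|---|
| One run | 5%; −7% to 8% | 5%; −7% to 9% |
| Random over 6 runs | 2%; −8% to 7% | 5%; −9% to 9% |
| Fully split | 7%; −50% to 27% | 3%; −38% to 25% |

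Exclusion of zero returns to 2-7% in every layout, which is compatible with 5% at 150 replicates. In the split layout the estimate stays imprecise because it leans on the control feeders, but the interval now reflects that. Experiment terms were fitted as fixed effects here; the random-intercept form was not simulated.

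**The case against.** The strongest reply is that the SAP already holds the right method. The section on inhibitory concentrations estimates SMFA activity for each participant and time-point against naive serum, "with random intercepts for each experiment to account for between experiments differences in oocyst intensity that is achieved in control experiments (SMFA"), and outcome 20 uses the same reference. The days listed for the generic model (1, 5, 14) match DMFA, while outcome 20 lists SMFA at days 0, 5, 14, 28, 56 and 84. The text looks as if it was written for the other assays, which would leave only a missing cross-reference. This reduces the severity but does not remove the conflict: the generic section names SMFA, claims all such analyses, and nothing says that the other section overrides it.

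A reader might also infer that day-0 and post-dose sera are likely to be in different runs. The SAP does not support that. It speaks of additional samples, not later ones, and places SMFA as a whole after unblinding, so all sera could be chosen and fed together. The layout is simply not fixed. Nor does the problem arise for every reference: if each sample is expressed against controls from its own run, the shared run effect cancels apart from control-feeder noise.

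The size of the problem is also open to challenge. A complete split is the extreme layout, and SMFA will cover only a sub-selection of samples, so 30 participants may be too many. With 10 participants, SE = √(1.1/200) = 0.074, and the R = 5, s = 0.3 case falls from 67% to about 48%. That still leaves a clear excess over 5%.

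Finally, keeping paired sera in one experiment may be settled in a laboratory procedure or the protocol, neither of which is shown. Its absence from the SAP is not a defect.

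**Conclusion.** The point holds as a conflict within the SAP with a conditional consequence. For SMFA, the section on transmission reducing activity fixes a day-0 contrast without experiment terms or controls, against outcome 20 and the section on inhibitory concentrations.

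The nominal 95% interval excludes zero under no effect in about 4-5% of trials if pairs share a run, 23-40% if samples are spread at random over six runs, and 67-91% if days are fully split, depending on the number of runs. These rates rest on the assumed inputs listed in the working, above all the between-run SD. With random spread the harm is intervals that are too narrow, not bias in one direction.

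It would go too far to say that run differences will be read as TB31F activity, or to quote the fully split rates as the expected error; the SAP does not establish that layout.

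The harm is confined to SMFA oocyst reduction, called exploratory in one section and listed as a secondary objective in another. The primary DMFA prevalence endpoint has its own model, and the IC80 work uses estimates that already carry an experiment term. Severity is minor to moderate.

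**What to change.** In the section on transmission reducing activity, take SMFA out of the generic model and refer it to the approach in the section on inhibitory concentrations:

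- a negative binomial model with an experiment random intercept;
- the naive-serum control feeders from the same runs included as their own sample type;
- the day contrast formed within that model.

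The controls are essential. If runs are split by day, an experiment intercept alone cannot separate run from day.

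Feeding a participant's day-0 and post-dose sera in one experiment is an optional laboratory step that would also recover precision.

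The cost is SAP wording. The control feeders are already planned, so no extra assays are needed. The change is best made before the SMFA runs are laid out.
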